2. STUDY OBJECTIVES

Phase I Primary Objective

1. To determine the safety, tolerability and RP2D of the combination of pegylated interferon with ixazomib.

Phase II Primary Objective

1. To determine progression free survival (PFS)

Phase II Secondary Objectives

1. To determine the composite rate of unacceptable toxicity at 8 weeks
2. To determine the overall response rate (ORR) using RECIST v1.1

Phase II Exploratory Objectives

1. To examine changes in STAT1 phosphorylation and MHC1 up regulation in PBMCs as an indicator of IFN activity
2. To use archived FFPE tumor tissue to correlate activated tissue stroma (i.e., desmoplasia) with serum IL-6 levels and patient outcomes
3. To use archived FFPE from past biopsies for IHC analysis of nuclear NF-κB p65 and phospho-STAT1 in order to test whether those patients with the most apparent constitutive pathway activation related to either of these two markers are generally more or less responsive to the combination therapy.

3. STUDY ENDPOINTS

Phase I Primary Endpoint

1. Presence or absence of dose-limiting toxicity during one cycle of pegylated interferon alpha with ixazomib.

Phase II Primary Endpoint

1. Progression free survival at 8 and 16 weeks using RECIST v 1.1.

Phase II Secondary Endpoints

1. Unacceptable toxicity rate at 8 weeks (any grade 5 toxicity, grade 4 neuropsychiatric toxicity or grade 4 clinically significant non-hematologic toxicity thought to be definitely, probably or possibly related to study drug)

2. Overall response rate at 8 and 16 weeks using RECIST v1.1.

[figure not shown]
Exploratory Endpoints for Phase I and II

1. To examine changes in STAT1 phosphorylation and MHC1 up regulation in PBMCs as an indicator of IFN activity
2. To use archived FFPE tumor tissue to correlate activated tissue stroma (i.e., desmoplasia) with IL-6 and patient outcomes
3. To use archived FFPE from past biopsies for IHC analysis of nuclear NF-κB p65 and STAT1.

4. STUDY DESIGN

The study will be conducted at a single center: Fox Chase Cancer Center. It will be open label and non-randomized. It will begin with a '3+3' phase I component to assess initial safety, tolerability and RP2D, followed by a phase II using a two-stage design previously described.⁴⁹ The design is meant to incorporate an early stopping rule for futility and toxicity, and to allow for an endpoint of PFS at 8 and 16 weeks rather than overall response. We believe PFS is a more valid endpoint given the scientific rationale of tumor necrosis rather than apoptosis resulting in radiographic disease stabilization rather than shrinkage. The overall treatment plan can be seen in Schedule of Events (page 6) and Figure 4-1.

Figure 4-1: Study Schema

4.1 Phase I: Dose Escalation

The first part of the study will be a phase I dose escalation enrolling at a minimum 12 candidates using a 3+3 stepwise design with doses for escalation and de-escalation and rules for each noted below in Table 4-1 and 4-2.

Evaluation will occur at C2D1 for toxicity, tolerability and dose-limiting toxicity during the first cycle for escalation decision. Treatment can continue indefinitely if beneficial (continual response or stable disease or symptomatic clinical benefit as defined by the

investigator) to patient. Evaluation at 8 and 16 weeks for efficacy and these patients may continue indefinitely as well if showing signs of clinical benefit.

Table 4-1: Dose escalation and de-escalation for phase I

Dose level	Ixazomib mg	Pegylated IFN μ g/kg/week
-2	2.3	2
-1	3	2
1 (starting dose level)	3	3
2	3	4.5
3 (expected RP2D)	4	4.5

Table 4-2. Escalation and De-Escalation Decision Rules

Number of Patients with DLT	Escalation/De-escalation Decision Rules
0 out of 3	
If dose level 1: Open dose levels 2.
 
If dose level 2: Open dose level 3.
 
If dose level 3: Declare this dose level the maximally administered dose (MAD). Move forward at this dose level to the expansion phase II.
 
If dose level -1 or -2: Dose level -1 or -2 will become the MTD and be used to move to phase II.

1 out of 3	
For all dose levels: Enter 3 more patients at this dose level.
 
If 0 of these 3 patients experience DLT, consider this dose acceptable and escalate to the next dose(s) as described above.
 
If another patient experiences DLT at this dose level (2 DLTs total), consider this dose unacceptable and the MAD. Declare the next lowest dose level(s) to be the MTD. If the MAD is dose level -2 and there are at least 2/6 DLTs the study will be halted for re-evaluation of lower dose levels.

≥ 2	
For dose level 3: Consider this dose unacceptable. Dose level 2 will become the MTD and be used to move to phase II.
 
For dose level 2: Consider this dose unacceptable. Dose level 1 will become the MTD and be used to move to phase II.
 
For dose level 1: Consider this dose unacceptable. De-escalate to dose level -1 and enroll additional 3 patients at dose level -1 followed by assessment as per above.
 
For dose level -1: Consider this dose unacceptable. De-escalate to dose level -2 and enroll additional 3 patients at dose level -2 followed by

	assessment as per above. If there are at least 2/6 DLTs the study will be halted for re-evaluation of lower dose levels.
--	--

The table below indicates the probability of dose escalation given various true DLT rates.

Probability of dose escalation.

	True Probability of DLT at Current Dose						
	0.10	0.20	0.30	0.40	0.50	0.60	0.70
Probability that dose is escalated	0.91	0.71	0.49	0.31	0.17	0.08	0.03

Only those patients that have received at least one dose of ixazomib will be counted for phase I analysis. If a patient stops the trial for reasons other than DLT in the first 28 days, they will be replaced for phase I analysis.

4.1.1 Definition of Dose Limiting Toxicity

Dose-limiting toxicity (DLT) is any drug related toxicity occurring during the first 28 days on study (cycle 1) that meets the parameters defined in Table 4-3.

Table 4-3. Dose Limiting Toxicity

Any grade 3 or 4 treatment related non-hematologic toxicity regardless of duration, except :

 Grade 3 nausea or Grade 3 vomiting \leq 72 hours that recovers to grade 0-2 with maximal antiemetic therapy. Grade 3 diarrhea that resolves to grade 0-2 with loperamide or diphenoxylate/atropine within 48 hours. Grade 3 hypercholesterolemia, hypertriglyceridemia, hyperglycemia or hypophosphatemia that resolves to grade 0-2 with medical management. Transient electrolyte abnormalities lasting \leq 1 week.
Grade 3 or 4 thrombocytopenia.
Grade 4 neutropenia associated with fever or hospitalization for infection.
Grade 4 neutropenia lasting longer than 5 days.
Any toxicity felt to be possibly or probably related to study medication that causes the patient to miss more than 1 dose of either Ixazomib or pIFN in the first 28 days.
Any unacceptable toxicity (UT) as defined for phase II below (Section 4.5)

4.3 Number of Patients

For the phase I portion of the study we will enroll at a minimum 12 and at a maximum 18 (please see Section 4.1 and 7 for more on the statistical design). For the phase II portion of the study we will enroll up to 31 patients. For phase II portion, a patient is considered enrolled at cycle 1 day 1 when at least one of the drugs has been administered. All patients will be included in the toxicity and PFS and RR analysis.

4.4 Duration of Study

From a study perspective, the anticipated duration of study being open for enrollment will be 2 years. Amongst Fox Chase Cancer Center and its community partners (FCCC) there were 450 analytic (new to the system without ever having had any treatment for their RCC) cases of RCC in 2012 alone and FCCC saw approximately 224 of those cases. Out of these cases at FCCC ~35/year were de novo metastatic and ~30/year were locally advanced and thus at high risk for short-term metastatic progression. In addition, ~30 non-analytic (primary treatment conducted elsewhere) cases per year were seen at FCCC sites.

According to the FCCC RCC database 256 nephrectomies were performed in 2010, 234 in 2011, 227 in 2012 and 204 in 2013. Over 75 new patients with RCC were seen by GU medical oncology in 2013 and over 43 patients with RCC were enrolled on therapeutic clinical trials. Given this volume of patients we believe we can accrue 1-2 patients a month to this trial.

Once an eligible patient is identified and consented, screening will occur within 28 days of study initiation (first day of drug administration). The patient will stay on study unless he or she has PD or unacceptable toxicity or chooses to withdraw consent. Once a patient is no longer on active treatment, follow up for progression and survival will occur for a maximum of 2 years.

4.5 Definition of Unacceptable Toxicity

For this study we will have a category defined as unacceptable toxicity (UT). This will be used in the statistical design of the phase II part of the study and incorporated into an early stopping rule (see Figure 7-1). If a patient develops UT at any point in the study, he or she will be withdrawn from the study. If more than 1 UT occurs during the final 6 patients of Phase I of the study, the study will be halted for assessment and possible amendment (Figure 7-1).

UT is defined as any grade 5 toxicity, grade 4 neuropsychiatric toxicity or grade 4 clinically significant non-hematologic toxicity thought to be definitely, probably or possibly related to study drug.

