8.1.2 Sample Size Determination

The design incorporates two conditions not usually treated. First, the final group of patients in the phase I component is considered part of the phase II trial. Second, the phase II part has two end-points, toxicity (UT: unacceptable toxicity) and efficacy. The relation between toxicity and efficacy is explicitly taken into account. We test the composite null hypothesis:

$H_0: p(UT) > 0.25 \text{ or } p(PFS > 8 \text{ weeks}) < 0.5 \text{ or } p(PFS > 16 \text{ weeks}) < 0.35$

versus the alternative:

$H_1: p(UT) < 0.05 \text{ and } p(PFS > 8 \text{ weeks}) > 0.66 \text{ and } p(PFS > 16 \text{ weeks}) > 0.56.$

Eleven new patients will be treated in the first stage of the phase 2 component. If 3/17 patients have UTs OR if at most 8/17 are alive and PF at 8 weeks the trial will be either be

suspended for excess toxicity or for futility. The decision for early termination (or amendment) is based on these cut points. If either 3 of 17 stage I patients are DLTs OR if at most 8 of 17 are PF at 8 weeks then terminate or hold up. The final decision point, PFS at 16 weeks is not relevant; the number of such patients does not influence the early decision. The confusion seems to relate to the alternative hypothesis which is couched in terms of 'AND'. It does, of course, require both early and late components of the outcome to be defined. Finally, although 3/17 is less than 0.25, this is the cut point, clearly between 0.05 and 0.25. The early PFS cut point 8/17 is less than 0.5 but is only a cut point.

At that point we will consider protocol amendment. Otherwise, 17 new patients will be recruited. If at least 14/34 patients are PF at 16 weeks AND less than 4/34 have UTs the null hypothesis will be rejected and the treatment declared efficacious. Otherwise it will be declared either too toxic or not efficacious.

Further operating characteristics and statistical details can be found in Appendix 12.3

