Illustrates how the joint event probabilities a, b, c and d at the end of the study relate. Namely, if we assign $a = 0.02$ then b, c and d can be determined by subtraction. Here we would get: $b = 0.54$, $c = 0.03$ and $d = 0.41$. For any value of a in $(0, 0.05)$ the other three terms are completely specified. In this design we are considering toxicity to be cumulative. We model the total chance of UT to occur with fraction f in the first interval (0, 8 weeks) and $1-f$ in the final 8 weeks. We have considered fractions $f = 0, 0.25, 0.5, 0.75$ and 1.0 , i.e. $f=0$ implies no toxicity in the first 8 weeks and $f = 1$ implies all toxicity occurs then. The final design is based on $f = \frac{1}{2}$.

P(UT)	1-p(UT)
a1	b1 p(PFS > 8) = 0.66
c1	d1 p(PFS < 8) = 0.34
ptox1	1 - ptox1 1 (ptox1 = ptox2 = 0.025 under the alternative with $f = \frac{1}{2}$) and
P(UT)	1-p(UT)
a2	b2 p(PFS > 16 PFS > 8) = 0.848
c2	d2 p(PFS < 16 PFS > 8) = 0.15
ptox2	1 - ptox2 1

The two tables above characterize the early stopping interval (0, 8 weeks) and final interval (8 weeks, 16 weeks). Numbers in the tables represent the alternative hypothesis. Patients in the initial cohort are represented by the top table (a1, b1, c1, d1) in the initial interval and those who are toxicity and progression free at 8 weeks, hence continue on study are represented by the second table (a2, b2, c2, d2) for their second 8 weeks. Patients recruited into the second cohort, if the study makes it past the first 8 week period, are evaluated only at 16 weeks and are represented by the very first table (a, b, c, d).

The chance of early stopping for excess toxicity, for futility, the chance of final declaration of excess toxicity, the power or type I error were all computed for each of the 4 conditions. Within each of these combinations, the fraction, f, of toxicity born within the first 8 weeks was varied in 5 steps from 0 to 1. We selected the number $f = \frac{1}{2}$ in the belief that toxicity is cumulative and this is the maximum fraction expected to occur in the first half of the trial. Design behavior for $f < \frac{1}{2}$ is ‘better’ than that for $f > \frac{1}{2}$, so is not reported here in detail.

The table below lists the various operating probabilities as functions of ‘a’ for each of the four conditions.

Key:

null = 0: PFS at 16 weeks = 0.35

null = 1: PFS at 16 weeks = 0.56

ntox = 0: Toxicity = 0.05

ntox = 1: Toxicity = 0.25

a: probability that PFS > 16 weeks and patient had UT

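### In the protocol text available, one drug-related death triggers no enrolment hold and no event-driven committee review

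*Combined protocol and SAP*

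**What the plan says.** **What a death counts as.** Section 4.5: "UT is defined as any grade 5 toxicity, grade 4 neuropsychiatric toxicity or grade 4 clinically significant non-hematologic toxicity", with attribution at least possible. Section 4.1.1: "Dose-limiting toxicity (DLT) is any drug related toxicity occurring during the first 28 days on study (cycle 1"), and Table 4-3 lists among the qualifying events "Any unacceptable toxicity (UT) as defined for phase II below (Section 4.5"). A related death is therefore one UT and, in cycle 1, also one DLT.

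**Phase I.** For one DLT in three patients, Table 4-2 says "For all dose levels: Enter 3 more patients at this dose level", and then "If 0 of these 3 patients experience DLT, consider this dose acceptable and escalate to the next dose(s) as described above".

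**Carry-over patients.** Section 4.5: "If more than 1 UT occurs during the final 6 patients of Phase I of the study, the study will be halted for assessment". For a single UT, the only action named is withdrawal of that patient.

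**Phase II.** Section 8.1.2 suspends the trial on this condition: "If 3/17 patients have UTs OR if at most 8/17 are alive and PF at 8 weeks". If it is not met, 17 more patients are recruited. The remaining toxicity limit, fewer than 4 UTs of 34, belongs to the final decision.

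**Oversight.** Sections 7.2.1 and 7.2.2 require a fatal serious adverse event to reach the drug supplier and the Study Monitor within 24 hours, the IRB under its own rules and, where reportable, FDA within 7 days. Section 8.1.6 says the Extramural Data Safety Monitoring Committee (EDSMC) will review safety data and may recommend ending accrual. The three-monthly interim analysis is optional, and the committee's duties are set out in a separate Data and Safety Monitoring Plan (DSMP). Section 10.2 lets the investigator deviate from the protocol to remove an immediate hazard.

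**The concern.** Read as written, the rules treat a drug-related death in the same way as a non-fatal DLT. In phase I they direct further dosing at the dose on which the patient died. In phase II they allow accrual to continue. A related death after day 28 in a phase I patient outside the final six enters no count rule at all; with 12-18 phase I patients that leaves 6-12 people in this position.

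This matters because the protocol cites no earlier experience with ixazomib plus pegylated interferon. Its closest precedent is bortezomib plus interferon in 16 melanoma patients. Section 1 also lists fatal interferon toxicities: neuropsychiatric events, pulmonary disorders, colitis and pancreatitis. At stake is whether the next few patients are dosed before anyone independent is required to ask if the death changes the risk.

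**Working it through.** **1. Which rules the design contains.** Appendix 12.3 puts half of the UT probability in the first 8 weeks, so p = 0.125 or 0.025 for 16-week rates of 0.25 or 0.05.

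- At least 3 of 17, no restriction on the first six: 1 - [(1-p)^17 + 17p(1-p)^16 + 136p²(1-p)^15] = 0.3591 and 0.0082, as printed.
- Given at most 1 UT in the first six: 0.2242/(1 - 0.1665) = 0.2690 and 0.005815/(1 - 0.008767) = 0.0059, as printed.
- Phase I escalation, (1-p)^3 + 3p(1-p)^5: at p = 0.10, 0.729 + 0.177 = 0.906. The remaining columns of the Section 4.1 table also reproduce.

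The modelled toxicity rules are therefore the counts alone, with no separate rule for a first death.

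**2. One death set against each rule.**

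| Rule | Count that triggers action | One related death |
|---|---|---|
| Table 4-2, one dose level | 2 DLTs | three more patients at the same dose |
| Section 4.5, final six of phase I | 2 UTs | no halt |
| Section 8.1.2, first 17 | 3 UTs | no halt |
| Section 8.1.2, second 17 | none during accrual | no halt |
| Section 8.1.2, all 34 | 4 UTs | final verdict only |

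A death that happens to be the second DLT at a dose level, or the second UT among the final six, does trigger action, but through the count. A death is also a PFS event, so it counts toward the 8/17 futility stop.

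**3. Patients exposed.** Section 4.4 expects 1-2 patients a month. The next patient arrives after about 0.5-1 month, and 3 × (1 to 2) = 3-6 arrive in three months. The upper figure is mainly for phase II. In phase I the next three patients take 1.5-3 months to enrol, and their 28-day window adds 0.92 month, so escalation would come 2.4-3.9 months after the death. A quarterly review, if held, would usually come first.

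**4. Chance of a further related death among those patients,** 1 - (1-d)^m, with the rate d taken as unchanged by the first death. The Clinical Safety Summary in Section 1 gives one ixazomib-related death. The denominator is 653 patients, or 530 without the 123 in a blinded study. The documents give no rate for interferon or for the combination, so 1% and 2% are assumptions.

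| d | m = 3 | m = 6 |
|---|---|---|
| 1/653 | 0.0046 | 0.0091 |
| 1/530 | 0.0056 | 0.0113 |
| 0.01 (assumed) | 0.030 | 0.059 |
| 0.02 (assumed) | 0.059 | 0.114 |

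**The case against.** The strongest objection is that two places where such a trigger would normally sit cannot be seen: the DSMP, and the flow diagram to which Section 4.5 refers for its stopping rule. This stands, and it limits the point to the visible text.

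The existing brakes are also real. Reporting is prompt, the committee does review safety data and can recommend ending accrual, and a cycle 1 death delays escalation until three more patients have been cleared. Counting a grade 5 event as one DLT or UT is consistent with the chosen 3+3 and two-stage rules. All of this stands. What it leaves open is the absence of any required pause or review when the event happens.

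Three stronger readings are tempting, and the documents do not support them.

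- *Second-stage patients go unmonitored until week 16.* Appendix 12.3 does say "Patients recruited into the second cohort, if the study makes it past the first 8 week period, are evaluated only at 16 weeks", but this describes which probability table represents them in the calculations. The schedule of events gives every patient adverse event monitoring from cycle 1 on. The missing second-stage halt follows from Section 8.1.2 alone.
- *A large probability of harm.* The chance of at least one related death among 34 patients with no toxicity halt is 0.29 at an assumed 1% and 0.49 at 2%. That is nearly the chance of any related death (0.29, 0.50). It shows how often a pause would be invoked, and not what its absence costs. It also ignores futility stopping. If half of trials stop at 17, the chance of any related death is 0.5 × 0.157 + 0.5 × 0.289 = 0.22, or 0.5 × 0.291 + 0.5 × 0.497 = 0.39.
- *Frequent escalation past a death.* The formula 3d(1-d)^5 gives 2.9% and 5.4% per cohort, but only if deaths are the sole DLTs. Grade 3-4 thrombocytopenia is also a DLT. Table 1-9 shows related grade 3 or higher thrombocytopenia in 19% of oral ixazomib patients (all cycles and doses, so indicative only). With a total DLT rate of 0.19, 3d(0.81)^5 gives 1.0% and 2.1%.

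**Conclusion.** The point holds for the visible text, as a safety rule worth adding at little cost. It is not an inferential error, and it does not show that oversight is absent.

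The practical size is about 3-6 further patients dosed in a quarter without a required committee judgement, mainly at the same dose. The chance of another related death among them is about 0.5-1.1% at the ixazomib rate, 3-6% at an assumed 1% and 6-11% at an assumed 2%. These figures rest on accrual as planned, independent patients and a rate that the first death does not alter. If the first death signals a higher risk than expected, they are too low.

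A reader might infer that no trigger exists anywhere. The file cannot show that, because the DSMP and the flow diagram are missing from it.

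**What to change.** In Table 4-2, Section 4.5 and Section 8.1.6, state for both phases: *Any grade 5 event at least possibly related to either drug pauses new enrolment and dose escalation until the EDSMC has reviewed it and recommended whether to resume; the review also covers whether patients on treatment continue dosing.*

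The event still counts as a UT and, in cycle 1, as a DLT, so every cut point stays as it is. If the DSMP already contains this trigger, cite it in those three places instead. In the same amendment, add grade 5 to the 8-week toxicity endpoint in the protocol summary and Section 8.1.1, which name only grade 4 events, unlike Sections 3 and 4.5.

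The cost is one sentence in an amendment and, if a related death occurs, an ad hoc meeting of an existing committee, a short accrual pause and a small added chance of stopping.

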As of 27 March 2013, a total of 32 on-study deaths were reported in the clinical studies. One of the 32 events was deemed by the investigator to be related to treatment with Ixazomib (pneumonia RSV in Study C16005). The most common cause of death was disease progression.

Potential Benefits

The clinical benefit of ixazomib continues to be studied in a comprehensive and global development plan that involves studies sponsored by Millennium. Ixazomib appears to show early signs of anti-tumor activity as evidenced by at least 50% reduction in disease burden in

some patients, including patients that have been heavily pretreated as well as those with newly diagnosed MM, and prolongs stabilization of the underlying disease in other patients across all ongoing trials. The preliminary findings are favorable when considering historical and currently available therapies for the patient populations evaluated. Though additional data are needed to characterize the clinical benefit of this drug, the emerging data supports expanded development of Ixazomib for the treatment of patients with advanced malignancy.

IFN- α -2b: Description, PK, PD, and safety data

Pegylated IFN- α -2b is a covalent conjugate of recombinant alfa interferon with monomethoxy polyethylene glycol (PEG). The biological activity of pIFN is derived from its interferon α -2b moiety. Interferons exert their cellular activities by binding to specific membrane receptors on the cell surface and initiate a complex sequence of intracellular events. These include the induction of certain enzymes, suppression of cell proliferation, immunomodulating activities such as enhancement of the phagocytic activity of macrophages and augmentation of the specific cytotoxicity of lymphocytes for target cells, and inhibition of virus replication in virus-infected cells. Interferon alfa upregulates the Th1 T-helper cell subset in *in vitro* studies. Please see Section 1790898588 for more background from the [name] lab.

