7 ADVERSE EVENTS

7.1 Definitions

7.1.1 Adverse Event Definition

Adverse event (AE) means any untoward medical occurrence in a patient or subject administered a pharmaceutical product; the untoward medical occurrence does not necessarily have a causal relationship with this treatment. An AE can therefore be any unfavorable and unintended sign (including an abnormal laboratory finding), symptom, or disease temporally associated with the use of a medicinal (investigational) product whether or not it is related to the medicinal product. This includes any newly occurring event, or a previous condition that has increased in severity or frequency since the administration of study drug.

An abnormal laboratory value will not be assessed as an AE unless that value leads to discontinuation or delay in treatment, dose modification, therapeutic intervention, or is considered by the investigator to be a clinically significant change from baseline.

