7.1.3 Severity Rating

The investigator will evaluate the severity of each adverse event. NCI Common Terminology Criteria for Adverse Events (CTCAE v.4.0) or study specific toxicity tables provided in the protocol define severity. If not included in CTCAE v.4.0, severity is expressed in numerical grade using the following definitions:

Grade 1: Mild-asymptomatic or mild symptoms; clinical or diagnostic observations only; intervention not indicated.

Grade 2: Moderate-minimal, local or noninvasive intervention indicated; limiting age appropriate instrumental ADL.

Grade 3: Severe-severe or medically significant but not immediately life-threatening; hospitalization or prolongation of hospitalization indicated; disabling; limiting self care ADL.

Grade 4: Life-threatening consequences; urgent intervention indicated.

Grade 5: Death related to AE

Attribution/Relationship to study drug:

Definite – clearly related

Probable – likely related

Possible – may be related

Unlikely – doubtfully related

Unrelated – clearly not related

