8.1.1 Definition of Phase II and exploratory endpoints and Analytic Plan

The phase II dose will be determined by an initial standard '3+3' phase I component as described in Section 4.1. Once a RP2D is reached, the phase II will begin.

Definition of phase II primary endpoint: Progression free survival at 8 and 16 weeks using RECIST v 1.1, defined from date of treatment initiation to date of progression according to RECIST or death, or is censored at the date of the last imaging. If patient is not evaluated at 8 and/or 16 weeks then the patient is not considered as alive and progression-free.

Definition of secondary outcomes/endpoints:

1. Composite of unacceptable toxicity at 8 weeks (grade 4 non-hematologic toxicity thought to be definitely, probably or possibly related to study drug)
2. Overall response using RECIST v1.1.

Definition of exploratory objectives:

1. Changes in STAT1 phosphorylation and MHC1 up regulation in PBMCs from baseline to week 2, 3, 7, EOT.
2. Degree of desmoplasia in archived FFPE tumor samples and change in serum IL-6
3. Degree of nuclear NF- κ B p65 and STAT1 in archived FFPE tumor samples

Analytic plan for primary and secondary objectives:

Kaplan Meier curves will be used to estimate the distribution of progression free survival, median survival, and 1-year survival. Proportions, 95% confidence intervals, will be used to characterize composite rate of unacceptable toxicity and overall response rate. All analyses are for estimation only, and no larger inference will be generated given the sample size of the study.

Analytic plan for exploratory objectives:

Pre- and post- treatment phosphorylation changes in pSTAT1 and MHC1 (flow data, the MFIs will be log10) and serum IL-6 will be analyzed by paired t-tests. Degree of desmoplasia and nuclear NF- κ B and STAT1 will be quantified using standard immunohistochemical methods. Statistical analysis for western blots and responders vs non-responders tumor immunohistochemistry will be performed using non-parametric Mann-Whitney test and/or paired t-tests.

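### Unacceptable toxicity has conflicting definitions: depending on the section and the reading, all deaths from adverse events, only drug-related deaths, or no deaths enter the 3/17 and 4/34 counts

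*Combined protocol and SAP*

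**What the plan says.** Two definitions of unacceptable toxicity (UT) are in use.

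- **With grade 5.** Section 4.5: "UT is defined as any grade 5 toxicity, grade 4 neuropsychiatric toxicity or grade 4 clinically significant non-hematologic toxicity". The sentence closes "or grade 4 clinically significant non-hematologic toxicity thought to be definitely, probably or possibly related to study drug". Section 3 and the secondary endpoint list in the Protocol Summary use the same three items.
- **Without grade 5.** Section 8.1.1: "Composite of unacceptable toxicity at 8 weeks (grade 4 non-hematologic toxicity thought to be definitely, probably or possibly related to study drug". The statistical methods part of the Protocol Summary says the same. Relatedness is required, grade 5 is absent, and the limit to clinically significant events is also gone.

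Section 7.1.3 grades death as "Grade 5: Death related to AE". Section 7.1.1 says of an adverse event that "the untoward medical occurrence does not necessarily have a causal relationship with this treatment".

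UT drives several rules. Section 8.1.2 suspends the trial at 3/17 UTs and requires for success at least 14/34 progression-free at 16 weeks and that "less than 4/34 have UTs the null hypothesis will be rejected". Section 4.5 uses UT for patient withdrawal and for a halt in the last six phase I patients. Table 4-3 makes every UT a dose-limiting toxicity. Appendix 12.3 assumes UT rates of 5% and 25%.

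**The concern.** In the three-item list nothing but grammar decides whether relatedness applies to grade 5 (or to grade 4 neuropsychiatric events). There is no comma before the clause, and grade 5 is introduced by the word any. Taken with Sections 7.1.1 and 7.1.3, a death from an adverse event unrelated to the drugs can be entered as a UT. Under Section 8.1.1, by contrast, even a drug-related death is not one.

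Both directions matter. Counting unrelated deaths uses up an allowance of only three events in 34 and scores one death twice, as a PFS failure and as toxicity. Counting no deaths leaves the most serious drug-related events out of the safety half of the composite test. Two people applying the plan to the same data could reach different conclusions about the regimen.

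**Working it through.** **Inputs.** Stop if at least 3/17 UTs or at most 8/17 progression-free at 8 weeks; succeed if at least 14/34 are progression-free at 16 weeks and fewer than 4/34 have a UT (Section 8.1.2). Under the alternative: UT 0.05, half of it by week 8; PFS 0.66 at 8 weeks and 0.56 at 16 weeks, so 0.56/0.66 = 0.848 for the second interval (Appendix 12.3). Here *a* is the probability that a patient has a UT and is progression-free at 16 weeks. I take *a* = 0, where the tabulated power is highest.

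**Reproducing the plan's figures** (appendix table without restriction on the first six patients).

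- Early toxicity stop: P(Bin(17, 0.025) ≥ 3) = 0.0082 and P(Bin(17, 0.125) ≥ 3) = 0.3591. Both match.
- Early futility stop under the alternative: 0.0821. Matches.
- Power, by exact enumeration: 17 patients classed at week 8 as progression-free, UT or neither; those progression-free without UT followed to week 16; then 17 new patients classed at week 16. The tabulated value is 0.8732. If weeks 8–16 UTs in the first 17 patients are left out of the final count, the result is 0.868 (the appendix-style count). If every UT is counted against 4/34, it is 0.842. I carry both.

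**Adding unrelated deaths.** Let *q* be the 16-week risk of a death not due to the drugs that is nevertheless counted as UT, half of it by week 8. The UT rate becomes 0.05 + *q* at 16 weeks and 0.025 + *q*/2 at 8 weeks. PFS rates stay the same, because a death is already a PFS failure.

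The documents give no early death risk for this population. One rate derivable from them is the ixazomib programme: 653 patients and 32 on-study deaths (Section 1, Clinical Safety Summary), of which "One of the 32 events was deemed by the investigator to be related to treatment with Ixazomib". That gives 31/653 = 4.7%.

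Second column: P(Bin(34, 0.05 + *q*) ≥ 4). Third: P(Bin(17, 0.025 + *q*/2) ≥ 3). Last two: the enumeration above with the new rates.

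| *q* | P(≥4/34 UT) | Early toxicity stop | P(declare efficacy), every UT counted | P(declare efficacy), appendix-style |
|---|---|---|---|---|
| 0 | 0.088 | 0.008 | 0.842 | 0.868 |
| 0.02 | 0.212 | 0.020 | 0.752 | 0.814 |
| 0.047 (31/653) | 0.426 | 0.047 | 0.585 | 0.699 |
| 0.05 | 0.446 | 0.050 | 0.569 | 0.686 |
| 0.10 | 0.771 | 0.131 | 0.275 | 0.425 |

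The *q* = 0 row is also the result if relatedness applies to every component and the true related rate is 5%.

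**The case against.** A reader might infer that the protocol, as punctuated, makes deaths from renal cancer count as UT. The documents do not support that.

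- The closing clause can govern all three items.
- The defined noun is toxicity, not adverse event, and no section says that progression is graded as toxicity.
- Table 4-3 absorbs every UT into dose-limiting toxicity, which Section 4.1.1 defines as drug related.
- Appendix 12.3 describes UT as severe toxicity that, if frequent, would dictate dose reduction or termination. Deaths from cancer do not fit that description.
- Section 8.1.1 requires relatedness.

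The related-only reading is therefore the more natural intention. But no section states it for grade 5, and the statistics section, which would be the natural place to settle it, drops grade 5.

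The objection to the size also has force. The 31/653 pools intravenous and oral studies in several cancers and amyloidosis over unstated exposure. Progression ends treatment (Section 6.13), so many cancer deaths would come after a patient has left study treatment and might never be recorded as UT. The *q* that enters the count could be well below the total death risk; at 2% the appendix-style count still gives 0.81.

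Finally, an all-cause count has a merit: it avoids investigator attribution of deaths in an open-label trial of a new combination. That would be a legitimate choice, but it would have to be stated and matched by the assumed rates.

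**Conclusion.** The firm defect is inconsistency. The Protocol Summary, Section 3 and Section 4.5 include grade 5 with unclear relatedness; Section 8.1.1 and the statistical part of the Summary require relatedness and omit grade 5. The variable behind both decision rules therefore has at least three possible contents.

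The power loss is conditional on the broad reading. With a true related rate of 5%, about 5% counted unrelated deaths raises the chance of failing the 34-patient toxicity count from 0.09 to about 0.45. At 4.7% the probability of declaring efficacy is 0.59–0.70 instead of 0.84–0.87, below the stated 80%. This assumes *a* = 0, half of the events by week 8, and deaths additional to the related UTs. The death rate is an assumption, so the table is a sensitivity range and not a forecast. If relatedness applies to every component, none of this loss arises.

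**What to change.** Reconcile both Protocol Summary entries, Section 3, Section 4.5 and Section 8.1.1 into one UT definition for the Section 8.1.2 counts and the secondary endpoint. State for each component, including grade 5 and grade 4 neuropsychiatric events, whether relatedness is required, and keep or drop the clinical-significance limit consistently. The choice should match what the assumed 5% and 25% rates describe. If those are drug-toxicity rates, relatedness belongs on every component of the statistical count. If an all-cause count is wanted, Appendix 12.3 needs recomputing with background deaths included in the UT rates.

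List all on-study deaths separately, with cause and attribution, for the monitoring committee.

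Section 4.5 also ties UT to patient withdrawal and the phase I halt. Whether those rules use the same definition is for the sponsor to decide; the text should say so either way.

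The cost is a few clauses and one listing, with no change to sample size or cut points under a related-only count. The downside is that the attribution of a death then rests on investigator judgement. The listing makes that judgement visible.
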